11.6.2.1.1 THS 2.2 vs CC

Only subjects in the Group-1 PK population will be included in the following analyses.

The secondary analysis of AUC_(0-∞), AUC_(0-t') and t_{1/2} will be performed on the natural log-transformed parameters using the same ANOVA model as used for the primary analysis. (Section 11.6.1 "Primary Analyses"). Only subjects in the Group 1 PK population who provide evaluable data for both the THS 2.2 and CC products will be included in the analyses.

Supportive analysis will be performed as described in Section 11.6.3 "Supportive/Sensitivity Analysis" in order to evaluate the sensitivity of THS 2.2 effect estimates to methods used for missing data by means of a mixed model approach, should there be 20% or more missing PK parameters.

• The analysis of t_{max} will be performed by calculating the difference for each subject (THS 2.2 - CC) and obtaining the Hodges-Lehmann (Hodges and Lehmann, 1963) 95% CI estimates. The median t_{max} for each product and the median difference between the products along with the 95% CI will be presented in the tables. Supportive analysis will be performed as described in Section 11.6.3 "Supportive/Sensitivity Analysis" in order to evaluate the THS 2.2 effect estimates on t_{max} adjusted for period, sequence, and subject within sequence.

The data will be presented in the below outputs:

TFL	Title
number	
TABLES	
15.2.4.1	Analysis of Secondary Pharmacokinetic Parameters of Nicotine –
	Group-1 PK Population

11.6.2.1.2 THS 2.2 vs NNS

The following analyses will be conducted in only Group-2 PK population:

• The secondary analysis of C_{max}, AUC_(0-last), AUC_(0-∞), AUC_(0-t') and t_{1/2} parameters will be performed using the same ANOVA model as used for the primary analysis. (Section 11.6.1 "Primary Analyses").

Only subjects in the Group-2 PK population who provide evaluable data for both the THS 2.2 and CC products will be included in the analyses.

Philip Morris Products S.A. Protocol ZRHR-PK-01-EU Statistical Analysis Plan Final v 3.0 / 08 May 2014 Confidential Page 47 of 72

The analysis of C_{max} and $AUC_{(0-last)}$ will test if the lower bound of the 95% CI for the ratio (THS 2.2 : NNS) is > 1.0 at the 0.025 level of significance in order to determine if the rate and the amount of nicotine absorbed of the THS 2.2 is higher relative to NNS. This approach will be used to test the following hypothesis for both C_{max} and $AUC_{(0-last)}$ parameters:

 $H_0: X_{THS} / X_{NNS} = 1.0 \\ H_A: X_{THS} / X_{NNS} > 1.0$

where X_{THS} and X_{NNS} are the adjusted geometrical means of THS 2.2 and NNS, respectively. H₀ is rejected with a type I error $\alpha = 0.025$ (one-sided test).

• To test if the time to the maximum nicotine concentration in THS 2.2 is shorter than in NNS the following hypothesis will be evaluated:

H₀: $X_{THS} - X_{NNS} = 0$ H_A: $X_{THS} - X_{NNS} < 0$

where X_{THS} and X_{NNS} are the median values of the THS 2.2 and NNS, respectively. t_{max} will be analysed on the original scale using the Wilcoxon Signed-Rank Test with a type I error $\alpha = 0.025$ (one-sided test), as values are ordinal/discrete, and the assumption of normality may be questionable.

The analysis of t_{max} will be performed by calculating the difference for each subject (THS 2.2 - NNS) and obtaining the Hodges-Lehmann 95% CI estimates (**Hodges and Lehmann, 1963**). The median t_{max} for each product and the median difference between the products along with the 95% CI will be presented.

Supportive analysis will be performed as described in Section 11.6.3 "Supportive/Sensitivity Analysis".

The data will be presented in the below outputs:

TFL number	Title
TABLES	
15.2.4.2	Analysis of Pharmacokinetic Parameters of Nicotine – Group-2 PK
	Population

11.6.2.2 Biomarkers

11.6.2.2.1 Exhaled CO and COHb

COHb measured in blood and exhaled CO will be investigated as a measure of exposure to CO.

CO in exhaled breath will be measured using the Smokerlyzer® device, such as the Micro+TM Smokerlyzer® device or similar, once on Day -1 and Day 4. On Days 1 and 3, the first test per day will be performed within 15 minutes prior to T_0 and then between

Philip Morris Products S.A. Protocol ZRHR-PK-01-EU Statistical Analysis Plan Final v 3.0 / 08 May 2014 Confidential Page 48 of 72

12:00 PM and 01:30 PM, between 4:00 PM and 05:30 PM, and between 8:00 PM and 09:30 PM. On the wash-out days (Day 0 and Day 2) it will be conducted between 08:00 AM and 09:30 AM, 12:00 PM and 01:30 PM, between 4:00 PM and 05:30 PM, and between 8:00 PM and 09:30 PM.

Analysis of the COHb measurement will be performed at a local laboratory using blood samples taken at specified timepoints. A total of 5 blood samples will be taken per single use day. The first sample will be taken within 15 minutes prior to T_0 . Thereafter the sampling times in relation to T_0 are at 15 minutes, 60 minutes, 4 hours, 12 hours post T_0 .

Descriptive statistics summarized by exposure will be produced separately for all scheduled timepoints for exhaled CO and COHb assessments at single use day. This will be done on the PK populations, overall and by the two stratification factors (sex, CC nicotine level at Admission) as specified in Section 11.1.1 "Stratified Presentation".

Actual values of blood COHb and levels of exhaled CO will be listed and summarized. The number of subjects with COHb levels $\leq 2\%$ will be summarized for each measurement. The 2% threshold is important because, as reported in (WHO, 2010), COHb elevated above 2% was found to cause ST-segment changes and decreased time to angina.

In addition line graphs will be produced for exposure means (and 95% CI) over all timepoints.

Values of exhaled CO measured during wash-out, Admission, and discharge will not be analyzed because they will be collected only for monitoring purposes, however they will be reported as described in Section 11.4 "Measurements of Product Compliance".

The analysis of the exhaled CO during single use and log transformed blood COHb levels will be performed using a mixed effects ANOVA with a restricted maximum likelihood (REML) method to estimate mean differences and variances separately for THS 2.2 vs CC and THS 2.2 vs NNS, using heterogeneous compound symmetry covariance structure in order to allow unequal variances at the different timepoints (**Brown and Prescott**, **1999**). Subject nested within sequence will be used as a random effect and sequence, period, product and product*time point as fixed effect factors. The model will be evaluated including all of the different assessment timepoints, excluding the assessment prior to T_0 , In addition, time point will be treated as a repeated measurement.

Philip Morris Products S.A.	Statistical Analysis Plan	Confidential
Protocol ZRHR-PK-01-EU	Final v 3.0 / 08 May 2014	Page 49 of 72

The SAS code to be used is shown below:

```
Proc mixed data=_data__ method=reml maxiter=200;
Class subject sequence product period;
Model log_COHb (or CO) = sequence period product time_point
product*time_point;
Random subject(sequence);
Repeated time_point / subject=subject*product type=csh;
Lsmean product / pdiff =control('CC/NNS') alpha=0.05 cl;
Lsmean product*time_point / pdiff alpha=0.05 cl;
Run;
```

In case of model convergence issues, this will be reported in the study report and additional covariance structures will be investigated with the following order: heterogeneous autoregressive(type=arh), variance component (type=vc), and unstructured (type=un).

For the analysis of CO breath test, the main comparison will be the difference over all time points. LS means for each product, the overall difference (THS 2.2 - CC or THS 2.2 - NNS as appropriate) and the differences at each time point will be presented in the tables as a point and interval (95% CI) estimate. Figures of the LS mean difference and 95% CI at each time point will be produced.

For the COHb analysis, the main comparison will be the ratio over all time points. LS means for each product will be back-transformed by exponantiation and presented in tables together with the point and interval (95% CI) estimate of the overall ratio (THS 2.2:CC or THS 2.2:NNS as appropriate) and of the ratios at the different time points. Figures of the LS mean ratio and 95% CI at each time point will be produced.

TFL number	Title
TABLES	
15.2.4.7	Analysis of Blood COHb (%) – PK Population
15.2.4.8.1	Descriptive Statistics of Blood COHb (%) Continuous Measurements –
	PK Population
15.2.4.8.1.1	Descriptive Statistics of Blood COHb (%) by Sex – PK Population
15.2.4.8.1.2	Descriptive Statistics of Blood COHb (%) by Nicotine Level – PK
	Population
15.2.4.8.2	Descriptive Statistics of Blood COHb (%) Categorical Measurements –
	PK Population
15.2.4.9	Analysis of Exhaled CO (ppm) During Single Use – PK Population
15.2.4.10.1	Descriptive Statistics of Exhaled CO (ppm) During Single Use
	Continuous Measurements – PK Population
15.2.4.10.1.1	Descriptive Statistics of Exhaled CO (ppm) During Single Use by Sex -
	PK Population

Philip Morris Products S.A. Protocol ZRHR-PK-01-EU Statistical Analysis Plan Final v 3.0 / 08 May 2014 Confidential Page 50 of 72

TFL number	Title
15.2.4.10.1.2	Descriptive Statistics of Exhaled CO (ppm) During Single Use by
	Nicotine Level – PK Population
15.2.4.10.2	Descriptive Statistics of Exhaled CO (ppm) During Single Use
	Categorical Measurements- PK Population
15.2.4.11.1	Descriptive Statistics of Exhaled CO (ppm) During Days -1, 0, 2 and 4
	Continuous Measurements – PK Population
15.2.4.11.1.1	Descriptive Statistics of Exhaled CO (ppm) During Days -1, 0, 2 and 4
	by Sex – PK Population
15.2.4.11.1.2	Descriptive Statistics of Exhaled CO (ppm) During Days -1, 0, 2 and 4
	by Nicotine Level – PK Population
15.2.4.11.2	Descriptive Statistics of Exhaled CO (ppm) During Days -1, 0, 2 and 4
	Categorical Measurements- PK Population
FIGURES	
15.1.2.6.1	Blood COHb (%) Profiles Geometric Mean (± 95% CI) – Group-1 PK
	Population
15.1.2.6.2	Blood COHb (%) Profiles Geometric Mean (± 95% CI) – Group-2 PK
	Population
15.1.2.7.1	Blood COHb (%) Profiles Geometric Least Squares Mean Ratio (± 95%
151050	CI) – Group-1 PK Population
15.1.2.7.2	Blood COHb (%)Profiles Geometric Least Squares Mean Ratio (± 95%
151001	CI) – Group-2 PK Population
15.1.2.8.1	Exhaled CO (ppm) Profiles During Single Use Arithmetic Mean ($\pm 95\%$
151202	CI) – Group-1 PK Population
15.1.2.8.2	Exhaled CO (ppm) Profiles During Single Use Arithmetic Mean (± 95%
15.1.2.9.1	CI) – Group-2 PK Population
13.1.2.9.1	Exhaled CO (ppm) Profiles During Single Use Arithmetic Least Squares Mean Differences (± 95% CI) – Group-1 PK Population
15.1.2.9.2	Exhaled CO (ppm) Profiles During Single Use Arithmetic Least Squares
13.1.2.7.2	Mean Differences (± 95% CI) – Group-2 PK Population
LISTINGS	Wean Differences $(\pm 9570 \text{ Ci}) = \text{Oroup-2 I K Topulation}$
15.3.3.4	Listing of Blood COHb Levels (%) and Sampling Times
15.3.3.5	Listing of Exhaled Breath CO (ppm) and Measurement Times
10.0.0.0	Listing of Exhause Dream CO (ppin) and Weasurement Times

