7.3.3 Questionnaire of Smoking Urges Brief

The QSU-brief (**Cox et al, 2001**). is a self-reported questionnaire completed 10 times at the following timepoints at Day 1 and Day 3:

- The first assessment will be done 15 min prior to T_0
- All other assessments will be done after T_0 , at T_0+15 minutes, T_0+30 minutes, T_0+45 minutes, T_0+1 hour, T_0+2 hours (with an allowed time window of +5 min each) and T_0+4 hours, T_0+6 hours, T_0+9 hours, T_0+12 hours (with an allowed time window of +10 min each).

Philip Morris Products S.A. Protocol ZRHR-PK-01-EU Statistical Analysis Plan Final v 3.0 / 08 May 2014 Confidential Page 25 of 72

The QSU-brief consists of 10 items as presented in Table 6.

Table 6: Questionnaire of Smoking Urges Brief - Questions and Factors

	Question	Factor
1	I have a desire for a cigarette right now	1
2	Nothing would be better than smoking a cigarette right now	2
3	If it were possible, I probably would smoke now	1
4	I could control things better right now if I could smoke	2
5	All I want right now is a cigarette	2
6	I have an urge for a cigarette	1
7	A cigarette would taste good now	1
8	I would do almost anything for a cigarette now	2
9	Smoking would make me less depressed	2
10	I am going to smoke as soon as possible	1

All items will be rated on a 7-point scale, ranging from 1 (strongly disagree) to 7 (strongly agree). Higher scores indicate a higher urge to smoke.

Two factor scores and a total score will be derived (**Cox et al, 2001**). Each factor is a subset that includes 5 of the 10 questions as defined in Table 6. Factor 1 represents the desire and intention to smoke with smoking perceived as rewarding, while Factor 2 represents an anticipation of relief from negative effect with an urgent desire to smoke.

The factors and total scores will be calculated by averaging non-missing item scores if at least 50% are non-missing, otherwise the factor or total score will be set to missing.

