11.6.2.3 Questionnaires

11.6.2.3.1 Urge-to-Smoke Questionnaire of Smoking Urges Brief

The total score and the two factors from the QSU-brief will be listed for all scheduled time points and summarized overall and by the two stratification factors (sex, CC nicotine level at Admission) for the PK populations, as specified in Section 11.1.1 "Stratified Presentation". The individual responses to all questions will be listed by product, study day, and assessment time points.

In addition line graphs will be produced for the total score and factors means (and 95% CI) over all timepoints.

Philip Morris Products S.A. Protocol ZRHR-PK-01-EU

Statistical Analysis Plan Final v 3.0 / 08 May 2014 Confidential Page 51 of 72

The analysis of the subjective effects of smoking (the total score, and Factor-1 and Factor-2 from the QSU-brief) will be performed using the same mixed effects ANOVA adopted for the analysis of CO breath test described in Section 11.6.2.2.1 "Exhaled CO and COHb".

A sensitivity analysis using bootstrap techniques, will also be conducted on the total and factors score of QSU-brief, as described in Section 11.6.3 "Supportive/Sensitivity Analysis".

The main comparison will be the mean difference over all timepoints. LS means for each product, the overall mean difference (THS 2.2 - CC or THS 2.2 - NNS as appropriate) and the mean differences at each time point will be presented in the tables as a point and interval (95% CI) estimate. Figures of the LS mean difference and 95% CI at each time point will be produced.

The data will be presented in the below outputs:

TFL number	Title
TABLES	
15.2.4.12	Analysis of QSU-brief Questionnaire Factors and Total Score – PK
	Population
15.2.4.14	Descriptive Statistics of QSU-brief Questionnaire Factors and Total
	Score – PK Population
15.2.4.14.1	Descriptive Statistics of QSU-brief Questionnaire Factors and Total
	Score by Sex – PK Population
15.2.4.14.2	Descriptive Statistics of QSU-brief Questionnaire Factors and Total
	Score by Nicotine Level – PK Population
FIGURES	
15.1.2.10.1	QSU-brief Factors and Total Score Profiles Arithmetic Mean (± 95% CI)
	– Group-1 PK Population
15.1.2.10.2	QSU-brief Factors and Total Score Profiles Arithmetic Mean (± 95% CI)
	– Group-2 PK Population
15.1.2.11.1	QSU-brief Factors and Total Score Profiles Arithmetic Least Squares
	Mean Differences (± 95% CI) – Group-1 PK Population
15.1.2.11.2	QSU-brief Factors and Total Score Profiles Arithmetic Least Squares

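### The log COHb and exhaled CO models leave out the pre-use value taken on each single-use day, which may cost precision in the product comparison

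*SAP*

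**What the plan says.** A pre-use value exists in every period for all three outcomes. In SAP 11.6.2.2.1, one of the five COHb samples per single-use day is pre-use ("The first sample will be taken within 15 minutes prior to" T0), as is one of the four breath tests on Day 1 and Day 3 ("the first test per day will be performed within 15 minutes prior to" T0). SAP 7.3.3 has ten QSU-brief assessments per single-use day, and "The first assessment will be done 15 min prior to" T0.

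For the COHb and CO model, SAP 11.6.2.2.1 states: "The model will be evaluated including all of the different assessment timepoints, excluding the assessment prior to" T0. The terms are listed as: "Subject nested within sequence will be used as a random effect and sequence, period, product and product*time point as fixed effect factors". The SAS statement, "Model log_COHb (or CO) = sequence period product time_point" plus the product-by-time interaction, likewise has no pre-use term. QSU-brief inherits the model: under SAP 11.6.2.3.1 its scores are "performed using the same mixed effects ANOVA adopted for the analysis of CO breath test".

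The readings are unused only in the models. They remain in the summaries and listings by time point, and pre-use CO is a compliance check (SAP 11.4).

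**The concern.** A random subject effect removes what is constant in a subject across both periods, and the period term removes the average shift between periods. Neither removes the part of the shift that differs between subjects. The two periods start from different histories: Day 1 follows ad libitum smoking on Day -1 and one washout, while Day 3 follows one product use and a second washout (SAP 6.1.1, 11.4). If a subject starts one period with a higher COHb or CO level, and that difference persists into the post-use readings, it enters the error of the THS 2.2 versus CC or NNS contrast.

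At stake is the width of the 95% intervals for the main COHb and CO comparisons, with 44 subjects in one group and 18 in the other. Settling the choice in advance also avoids choosing between adjusted and unadjusted results after the data are seen.

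**Working it through.** **1. Numbers of completers.** The SAP gives no precision figure for COHb, CO or QSU-brief, so the completer numbers come from its Cmax sizing in section 8 (CV 36%, 10% dropout).
- SD of the paired log difference: sqrt(2 × ln(1 + 0.36²)) = 0.494.
- THS 2.2 vs CC: the probability that the 95% half-width is at most ln(1.2) is 0.897 with 39 completers and 0.920 with 40. So 40 are needed. Dropout gives 40 × 1.1 = 44, or 40/0.9 = 44.4, rounded up to 45. The stated 44 is reproduced within rounding convention.
- THS 2.2 vs NNS: paired t power for ln(1.55) is 0.912 with 16 completers, and 16/0.9 = 17.8, rounded up to 18. The stated 18 is reproduced.

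The calculation below uses 40 and 16 completers.

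**2. Set-up.** In a 2x2 crossover, each subject's difference between products (averaged over post-use time points) is free of the subject effect. Without adjustment, the contrast has n - 2 degrees of freedom. Entering the pre-use value together with the subject's mean pre-use value is equivalent, for this contrast, to regressing the post-use difference on the pre-use difference, with n - 3 degrees of freedom. Let r be the correlation of those two differences; it is an assumption.

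- Variance ratio, adjusted to unadjusted: (1 - r²) × (1 + 1/(n - 4)). The second factor is the cost of estimating the slope.
- CI width ratio: square root of the variance ratio × t(0.975, n - 3)/t(0.975, n - 2).

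**3. Worked case, r = 0.5.**
- n = 40: variance ratio 0.75 × (1 + 1/36) = 0.771; width ratio sqrt(0.771) × t(37)/t(38) = 0.879.
- n = 16: variance ratio 0.75 × (1 + 1/12) = 0.812; width ratio sqrt(0.812) × t(13)/t(14) = 0.908.

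| r (assumed) | Width ratio, n = 40 | Acts like | Width ratio, n = 16 | Acts like |
|---|---|---|---|---|
| 0 | 1.015 | 38.8 | 1.048 | 14.6 |
| 0.2 | 0.994 | 40.5 | 1.027 | 15.2 |
| 0.3 | 0.968 | 42.7 | 1.000 | 16.0 |
| 0.5 | 0.879 | 51.8 | 0.908 | 19.4 |
| 0.7 | 0.725 | 76.2 | 0.749 | 28.5 |

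The column headed Acts like is n divided by the squared width ratio. Setting the width ratio to 1 gives the break-even r: 0.17 for n = 40 and 0.30 for n = 16. Simulation of the paired-difference model agrees (at r = 0.5: 0.878 and 0.905).

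**4. The form of adjustment matters.**
- A change-from-pre-use score has variance ratio 2(1 - r) if the SDs are equal. It doubles the variance at r = 0 and breaks even only at r = 0.5.
- The raw pre-use value alone beside a random subject effect mixes between- and within-subject slopes. In a small simulation (150 runs per setting, strong between-subject association assumed), the SE of the product effect rose about 20% when the within-subject slope was 0 and fell only about 4% when it was 0.5. Adding the subject mean separates the two slopes.

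**The case against.** The exclusion is explicit and prespecified, and text and code agree on it. The random subject effect already removes stable between-subject variation. These endpoints are descriptive (SAP 5.2), lie outside the success criterion (5.4.2) and support no claim (11.1.7). All of that stands and limits the weight of the point.

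There are also reasons to expect a modest r. The main comparison averages over all post-use time points, COHb runs to 12 hours, and the first post-use breath test is at 12:00 PM or later while T0 is no later than 9:00 AM. Both pre-use readings follow a washout, and CO above 10 ppm before use counts as non-compliance, which narrows the spread. This also stands: the documents do not show that r exceeds break-even, especially in Group-2.

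Three stronger readings are tempting but unsupported:
- A reader might infer that adjustment is free because the data are already collected. It is not: below the break-even r the interval widens.
- A reader might infer that carry-over biases the unadjusted contrast and that adjustment would remove part of the bias. Sequence is randomized, period is in the model, and nothing in the SAP shows carry-over in CO or COHb. The version 3.0 revision entry reports unexpectedly high pre-use nicotine in some subjects, but that is a different analyte. If the Day 1 product did alter the Day 3 starting value, the covariate would itself be affected by treatment and would need its own justification.
- A reader might extend the adjustment to the main QSU-brief model. Randomization is on Day 0 (SAP 6.1) and allocation is open thereafter (6.3.2), so both pre-use craving ratings are given with the product known. Adjusting could remove part of a product-related difference. This concern is much weaker for COHb and CO, which are physiological measurements under confinement.

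**Conclusion.** The point holds for log COHb and exhaled CO as a matter of precision. The models omit an available period-specific covariate, and within-subject differences in starting level stay in the error of the product contrast. No bias is demonstrated.

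The possible gain is larger than the possible loss, but neither is certain. At r = 0.5 the intervals would be 12% narrower in Group-1 and 9% narrower in Group-2. At r = 0 they would be 1.5% and 4.8% wider. In Group-2 nothing is gained until r exceeds about 0.30. These figures assume 40 and 16 completers, complete pairs and one slope common to all post-use time points. The value of r is unknown from the documents. For QSU-brief, only a sensitivity analysis is warranted.

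**What to change.** In SAP 11.6.2.2.1, add to the log COHb and exhaled CO models the subject's pre-T0 value for that period (log scale for COHb) and the subject's mean pre-T0 value over both periods, keeping all other terms. The pre-T0 reading stays out of the response. In SAP 11.6.3, add the same adjustment for the three QSU-brief scores as a sensitivity analysis only, with the open-label timing of the rating given as the reason. If the sponsor prefers not to adjust COHb and CO, a sentence of justification should be added.

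The cost is a few lines of text and code, no new data, and one degree of freedom for the within-subject slope. The downside is a slightly wider interval if r is below break-even. SAP section 3 allows amendment before database lock.

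### The mixed model for exhaled CO, COHb and QSU-brief names no degrees-of-freedom method, so its main 95% CIs come out somewhat too narrow, and the VC step in its fallback could understate the error much more

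*SAP*

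**What the plan says.** SAP section 11.6.2.2.1 analyses exhaled CO and log COHb, separately for THS 2.2 vs CC and THS 2.2 vs NNS, with code that opens "Proc mixed data=_data__ method=reml maxiter=200". Neither that line nor the MODEL statement has a DDFM option, and the text gives no degrees-of-freedom method.

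The subject effect is "Random subject(sequence"). The within-period structure is "Repeated time_point / subject=subject*product type=csh". The CLASS list, "Class subject sequence product period", omits time_point.

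The main comparison is the product difference (CO) or ratio (COHb) over all post-use time points, requested by "Lsmean product / pdiff =control('CC/NNS') alpha=0.05 cl".

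The fallback is conditional and disclosed: "In case of model convergence issues, this will be reported in the study report". As to which structures come next, the same sentence fixes a sequence of three: "additional covariance structures will be investigated with the following order: heterogeneous autoregressive(type=arh), variance component (type=vc), and unstructured (type=un".

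Under section 11.6.2.3.1 the QSU-brief total and factor scores follow suit. Their analysis "will be performed using the same mixed effects ANOVA adopted for the analysis of CO breath test described in" that same place, and the main comparison is again the mean difference over all time points. Section 11.6.3 adds a percentile bootstrap for QSU-brief and MCEQ, but nothing similar for CO or COHb.

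**The concern.** Each subject gives one pair of periods to the overall product comparison, however many readings are taken within a period. The information about its error therefore grows with the number of subjects, not the number of readings. The plan departs from this in two places:

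- **Degrees of freedom.** A default that counts every reading gives too small a t multiplier. This affects the planned model itself and needs no convergence failure.
- **VC fallback.** VC on the REPEATED side makes readings within a period independent given the subject intercept. The subject-by-product variation, which drives the error of the product comparison, is then missing from the SE. The unequal variances for which CSH was chosen are lost too.

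What is at stake is the 95% CI of the stated main comparison for three secondary endpoints. The QSU-brief analysis is also among the topline results (section 12.3).

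**Working it through.** **Inputs**
- Subjects: 44 (Group-1) and 18 (Group-2) randomized, with 10% dropout (section 8).
- Post-use readings per period, T: CO 4 − 1 = 3; COHb 5 − 1 = 4; QSU-brief 10 − 1 = 9 (sections 7.3.3 and 11.6.2.2.1; Appendix 15.1). The pre-use value is excluded from the model.
- Two-sided 95% intervals.
- Assumption: with a RANDOM statement and no DDFM option, PROC MIXED uses containment. This is general software knowledge and is not in the SAP.
- Assumption: residual correlation ρ within a period, beyond the subject intercept. The SAP gives none, so a range is shown.

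**Step 1: the plan's sample sizes.** The SD of the paired log difference is √(2·ln(1 + 0.36²)) = 0.4937.
- Group-1: the smallest n with at least 90% probability of a half-width ≤ ln 1.2 is 40 (probability 0.92). 40 × 1.1 = 44, the plan's figure; 40/0.9 rounds up to 45.
- Group-2: a one-sided 0.025 test with ratio 1.55 needs n = 16 (power 0.912). 16/0.9 rounds up to 18, as stated.

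The plan's figures reproduce, and n = 40 and n = 16 evaluable are used below.

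**Step 2: degrees of freedom with CSH kept.** The random effect subject(sequence) does not contain product, so product gets the residual df:

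df = 2nT − rank[X Z], where rank = n + 1 (period) + 1 (product) + (T−1) + (T−1) = n + 2T.

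The rank was confirmed numerically. Example, Group-2 QSU-brief: 2·16·9 − (16 + 18) = 288 − 34 = 254.

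The subject-level df come from analysing the 2n period means: 2n − (n + 2) = n − 2. Coverage is P(|t(n−2)| < t crit of the residual df).

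| Group, endpoint | default df | n − 2 | t used / t needed | too narrow by | coverage |
|---|---|---|---|---|---|
| 1, CO | 194 | 38 | 1.972 / 2.024 | 2.6% | 94.4% |
| 1, COHb | 272 | 38 | 1.969 / 2.024 | 2.7% | 94.4% |
| 1, QSU-brief | 662 | 38 | 1.964 / 2.024 | 3.0% | 94.3% |
| 2, CO | 74 | 14 | 1.993 / 2.145 | 7.1% | 93.4% |
| 2, COHb | 104 | 14 | 1.983 / 2.145 | 7.5% | 93.3% |
| 2, QSU-brief | 254 | 14 | 1.969 / 2.145 | 8.2% | 93.1% |

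If nobody drops out (44 and 18), the narrowing is 2.3-2.7% and 6.2-7.2%.

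**Step 3: if VC is reached.** In units of the residual variance, a period mean has true variance [1 + (T−1)ρ]/T. VC replaces the bracket by the pooled within-subject mean square:

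SE ratio = √{ [1 + (T−1)ρ + 2(T−1)(1−ρ)] / [(2T−1)(1 + (T−1)ρ)] }.

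Example, QSU-brief at ρ = 0.1: √{(1.8 + 14.4)/(17 × 1.8)} = √0.529 = 0.73.

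| Endpoint | SE ratio at ρ = 0 / 0.1 / 0.3 / 0.5 | coverage at ρ = 0.1 / 0.3 / 0.5 |
|---|---|---|
| CO | 1 / 0.89 / 0.74 / 0.63 | about 92 / 85 / 78% |
| COHb | 1 / 0.86 / 0.68 / 0.56 | about 91 / 82 / 72% |
| QSU-brief | 1 / 0.73 / 0.50 / 0.39 | about 85 / 67 / 55% |

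Coverage comes from 40,000 simulated trials per cell and is nearly the same in both groups. A small REML check (COHb, ρ = 0.5, 200 runs per group) gave SE ratios of 0.56-0.57 and coverage of about 78%, with a Monte Carlo error of about 3 points.

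**The case against.** The strongest defence is that the planned model is nearly sound. CSH on subject*product keeps the within-period correlation, so the SE is right and only the t multiplier is off: at most 8% in interval width, and under 2 points of coverage. The larger losses need CSH to fail, ARH to fail, VC to be adopted, and a residual correlation that the SAP does not state. The SAP requires convergence problems to be reported, so a switch would not be silent. For QSU-brief, the worst case in Step 3, the bootstrap preserves subjects per sequence. If subjects are the resampling unit, as that implies, its interval depends on neither the df nor the VC choice. The objectives for these endpoints are descriptive (section 5.2), and section 11.1.7 says no claims rest on individual tests.

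All of this stands and limits the point. It does not remove it. The code is headed as the code to be used, and running it under the default gives intervals below nominal coverage. The bootstrap is aimed at distributional assumptions, and CO and COHb have none. Where the interval is the reported result, its coverage matters even without a claim.

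Some stronger readings are tempting but unsupported:
- A reader might infer that the fallback discards all within-period correlation. It does not: ARH comes first and keeps it, and the random subject intercept remains even under VC.
- A reader might infer that the planned intervals are grossly too narrow. That would need VC and a non-zero ρ.
- A reader might fault ARH for assuming equal spacing. That does not fit exhaled CO, whose post-use windows start four hours apart.
- The CLASS omission narrows no interval. It is a slip that would surface when the code is run.

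**Conclusion.** The point holds in two parts of different weight.

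1. Under the containment default, the overall product CIs are about 7-8% too narrow in Group-2 and about 3% too narrow in Group-1, with CSH retained. The effect is modest but systematic. It rests on the software default and on 40 and 16 evaluable subjects; full completion changes it little.
2. The fallback order is badly chosen. VC removes the correlation that governs the main comparison. It almost always converges (again general software knowledge), so UN, listed after it, would rarely be reached. The possible loss of SE is large but conditional on two convergence failures and on ρ, and it is nil at ρ = 0.

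The affected results are descriptive secondary comparisons. The primary analysis of C_max and AUC(0-last) uses a different model (section 11.6.1) and is not touched.

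**What to change.** In section 11.6.2.2.1, and so for QSU-brief through section 11.6.2.3.1:

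- Add ddfm=kr to the MODEL statement and name the method in the text.
- Take VC out of the fallback, or allow it only with a random subject*product term. One suitable order is CSH, ARH, then homogeneous CS on subject*product. This keeps the LS means at each time point, which section 9 and the planned figures need.
- Add time_point to CLASS, and list its main effect in the text as the code does.
- If wanted, analyse each subject's mean over post-use times with the 2x2 ANOVA, but only as a supplementary check of the overall contrast. It cannot give time-point estimates, and it would lose subjects with one use day if the primary analysis's both-products rule is applied.

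The cost is a few lines of text and code and slightly wider intervals. The change should be made before unblinding.
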